6.8.1 Pharmacokinetic samples (Subset of patients)

Approximately 150 patients randomised to olaparib/placebo, at pre-agreed sites will have PK assessment samples taken. PK sampling will not be done in the US.

6.8.2 Collection of samples

PK samples are to be taken as a blood sample (2 mL) for determination of olaparib concentrations in plasma. It is essential that PK blood sampling is conducted within the protocol sample collection windows indicated above.

To ensure that the assessments are carried out in the correct order, and that PK sampling is conducted within the required sampling window, it will be necessary to arrange the assessment procedures so that the PK assessments fall on/around the correct timing (see [Section 6.8](#)). The actual time of dosing and collection of all PK samples must be recorded as described below:

It is essential that the time of all 5 PK samples is recorded and that the times of the morning and evening dose on the day of PK sampling and the time of dose the evening before is recorded.

For blood volume see [Section 7.1](#).

6.8.3 Determination of drug concentration

Samples for determination of olaparib concentrations in plasma will be analysed by Covance on behalf of Clinical Bioanalysis Alliance, AstraZeneca R&D, using an appropriate bioanalytical method. Full details of the analytical method used will be described in a separate bioanalytical report. Placebo samples will not be analyzed unless specified.

6.9 Health economics

6.9.1 Resource use (serious adverse events)

Resource use for serious adverse events (including hospitalisations) will be captured through the adverse reporting procedures described in [Section 6.4](#).

7. BIOLOGICAL SAMPLING PROCEDURES

7.1 Volume of blood

The volume of blood that will be drawn from each patient will vary, dependent upon the length of time that the patient remains in the trial and if the patient is in the subset having PK samples taken. However, the total volume of blood to be drawn from each patient in the study (including for PK samples), assuming they complete screening, 12 months of treatment, a treatment discontinuation visit and the 30-day follow-up visit, should not exceed 208 mL.

Safety laboratory assessments will be performed locally at each centre's laboratory by means of their established methods. The number of samples/blood volumes is therefore subject to site-specific change.

Extra blood samples may also be collected if, for example, additional samples are required for repeat safety assessments or *BRCA* testing.

The total volume of blood that will be drawn from each patient in this study is as follows:

Table 13 Volume of blood to be drawn from each patient

Assessment	Sample volume (mL)	No. of samples	Total volume (mL)
Safety	Clinical chemistry	5	13
	Haematology	5	13
	Coagulation	5	1
Whole blood sample for Myriad BRCA test (retrospective/prospective)	9	1	9
Whole blood sample for assessment of current and future BRCA mutation assay(s)	9	1	9
Pharmacogenetics (optional)	9	1	9

Assessment	Sample volume (mL)	No. of samples	Total volume (mL)
Serum Pregnancy test	Site dependent	Site may use urine instead	
Serum sample for exploratory biomarkers, day 1 (mandatory)	6	1	6
Plasma sample for exploratory biomarkers, day 1 (Mandatory)	6	1	6
Serum sample for exploratory biomarkers, 30 days post study treatment discontinuation (Mandatory)	6	1	6
Plasma sample for exploratory biomarkers, 30 days post study treatment discontinuation (Mandatory)	6	1	6
Plasma sample for exploratory biomarkers, disease recurrence (Mandatory)	6	1	6
Serum sample for exploratory biomarkers, disease recurrence (Mandatory)	6	1	6
Pharmacokinetic (Blood samples processed to plasma & frozen) (Optional)	2	5	10
Total			208

7.2 Handling, storage and destruction of biological samples

The samples may be used up, disposed of after analyses or retained for further use as described here.

Biological samples for future research will be retained at the study bio-repository for a maximum of 15 years following the Last Patient's Last Visit in the study. The results from future analysis will not be reported in the Clinical Study Report but separately in a Scientific Report.

Biosamples collected for this study will be stored in study specific bio-repositories that are under the guardianship of BIG (non-US samples) and NRG Oncology and NCI (US samples) on behalf of the study Steering Committee.

7.2.1 Pharmacogenetic samples

The processes adopted for ensuring confidentiality of samples for genetic analysis are important. Samples will be stored for a maximum of 15 years, from the date of the Last Patient's Last Visit, after which they will be destroyed. DNA is a finite resource that may be used up during analyses. Samples will be stored and used until no further analyses are possible or the maximum storage time has been reached.

DNA will be extracted from the blood sample. The DNA sample will be assigned a unique number replacing the information on the sample tube. Thereafter, the DNA sample will be identifiable by the unique DNA number only. The DNA number is used to identify the sample

and corresponding data at the AstraZeneca genetics laboratories, or at the designated contract laboratory. No personal details identifying the individual will be available to any person (AstraZeneca employee or contract laboratory staff working with the DNA.)

The samples and data for genetic analysis in this study will be single coded. The link between the patient enrolment/randomisation code and the DNA number will be maintained and stored in a secure environment, with restricted access within the Clinical Genotyping Group Laboratory Information Management System (LIMS) at AstraZeneca. The link will be used to identify the relevant DNA samples for analysis, facilitate correlation of genotypic results with clinical data, allow regulatory audit and to trace samples for destruction in the case of withdrawal of consent when the patient has requested disposal/destruction of collected samples not yet analysed.

7.2.2 Pharmacokinetic samples

Pharmacokinetic samples will be disposed of after the Bioanalytical Report finalisation or six months after issuance of the draft Bioanalytical Report (whichever is earlier), unless requested for future analyses. Additional analyses may be conducted on the anonymised, pooled pharmacokinetic samples to further evaluate and validate the analytical method. Any results from such analyses will be reported separately from the Clinical Study Report (CSR).

Sample reproducibility analysis, if any, will be performed alongside the bioanalysis of the test samples. The results from the evaluation will not be reported in the CSR but separately in a Bioanalytical Report. Anonymised samples will be retained for no longer than 12 months after the Bioanalytical Report is finalised.

7.3 Labeling and shipment of biohazard samples

The Principal Investigator should ensure that samples are labelled and shipped in accordance with the B-55/6-13 Pathology and Correlative Science Instructions and the Biological Substance, Category B Regulations (materials containing or suspected to contain infectious substances that do not meet Category A criteria), see [Appendix B](#) ‘IATA 6.2 Guidance Document’.

Any samples identified as Infectious Category A materials should not be shipped and no further samples will be taken from the patient unless agreed with AstraZeneca/NRG Oncology/BIG or partners and appropriate labelling, shipment and containment provisions are approved.

7.4 Chain of custody of biological samples

A full chain of custody is maintained for all samples throughout their lifecycle.

The Principal Investigator at each centre is responsible for ensuring full traceability of collected biological samples from the patients while in storage at the centre until shipment or disposal (where appropriate).

The sample receiver keeps full traceability of the samples while in storage and during use until used or disposed of or until further shipment and keeps documentation of receipt of arrival.

AstraZeneca/NRG Oncology/BIG and their Partners keep oversight of the entire life cycle through internal procedures, monitoring of study sites and auditing of external laboratory providers.

Biosamples collected for this study will be stored in study specific bio-repositories that are under the guardianship of BIG (non-US samples) and NRG Oncology and NCI (US samples) on behalf of the study Steering Committee.

Samples retained for further use are registered in the bio-repositories systems during the entire sample life cycle.

If required, the remaining biological samples are returned to the site, according to local regulations or at the end of the retention period, whichever is the sooner.

7.5 Withdrawal of informed consent for donated biological samples

If a patient withdraws consent to the use of donated biological samples, the samples will be disposed of/destroyed, and the action documented. If samples are already analysed, AstraZeneca/NRG Oncology/BIG and their Partners are not obliged to destroy the results of this research.

BRCA sample: As collection of the biological samples is an integral part of the study, then the patient is withdrawn from further study participation.

Archival tumour sample: Although mandatory*, the patient may continue in the study if the patient is already randomised.

*For adjuvant patients, this refers to the surgical specimen; for neoadjuvant patients, both the pre-treatment core biopsy and the surgical specimen with residual disease are requested but only one is mandatory. If the surgery tumour blocks are available, but cannot be submitted, sites may submit a portion of invasive tumour from the original block, either by taking at least one core of at least 3 mm in diameter, or by splitting the original block in two parts, and re-embedding one in a new block for central submission. If blocks containing pre-neoadjuvant treatment core biopsies are available but cannot be submitted, sections mounted on glass slides prepared from the block can be provided. If tumour sample can't be provided as requested above or if it's not available, approval by Study Team for patient's entry into the trial is required.

Tumour samples at relapse: As collection of the biological samples is an optional part of the study, then the patient may continue in the study.

Pharmacokinetic samples: As collection of the pharmacokinetic samples is an optional part of the study, then the patient may continue in the study.

Blood samples for biomarker analysis (e.g. cfDNA): Collection of the biological samples is a mandatory part of the study, however, the patient may continue in the study despite withdrawing consent for analysis of the biomarker samples.

Blood sample for pharmacogenetic analysis: As collection of the biological samples is an optional part of the study, then the patient may continue in the study.

The Principal Investigator/site staff:

- Should ensure that NRG SDMC is notified immediately of a patients' withdrawal of informed consent for the use of donated samples
- Should ensure that biological samples from that patient, if stored at the study site, are immediately identified, disposed of /destroyed, and the action documented
- Should ensure that the laboratory(ies) holding the samples is/are informed about the withdrawn consent immediately and that samples are disposed/destroyed, the action documented and the signed document returned to the study site
- Should ensure that the patient and study representative are informed about the sample disposal.

The study representative ensures that the central laboratory(ies) holding the samples is/are informed about the withdrawn consent immediately and that samples are disposed of/destroyed and the action documented and returned to the study site.

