5.9 Withdrawal from study

Patients are at any time free to withdraw from the study (study treatment and assessments), without prejudice to further clinical care (withdrawal of consent). Such patients should always be asked about the reason(s) and the presence of any adverse events. If possible, they will be seen and assessed by an investigator. Adverse events will be followed up (See [Sections 6.4.9](#) and [6.4.10](#)); questionnaires (e.g. for patient reported outcomes) and all study drugs should be returned by the patient.

Withdrawn patients will not be replaced.

Reasons for withdrawal from the study:

- Voluntary withdrawal by the patient who is at any time free to discontinue their participation in the study, without prejudice to further treatment*
- Incorrectly enrolled patients i.e., the patient does not meet the required inclusion/exclusion criteria for the study – this option is only applicable to patients not randomised into the study (i.e. screen failures identified prior to randomisation)
- Patient lost to follow-up
- Death

*If a patient decides at any point in the trial that they do not wish to continue with the full study schedule of assessments but are still willing to provide important study information (e.g. disease recurrence information and/or survival status information) then the patient should continue in the study and information should continue to be collected in the eCRF. However, if a patient does not wish to have any further data collected, only then should they be considered as withdrawing consent from the study. To minimise the number of cases of early withdrawal the investigator should discuss the options with the patient to see if they would still be willing to provide

information on the important study endpoints (disease recurrence and overall survival), in which case they would remain in the study.

If a patient withdraws consent (i.e. nor further assessment or collection of their data), he/she should be specifically asked if they are also withdrawing consent to the use of any of their samples (tumour and blood) taken during the trial (see [Sections 6.6, 6.7](#) and [6.8](#)).

Data obtained prior to withdrawal of consent will be maintained in the clinical database and used in the study reporting.

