6.6.2 Collection of blood sample for Myriad germline *BRCA1* and *BRCA2* testing

Two blood samples are mandated for all patients. One sample will be used to test for *BRCA* mutations using the current commercial Myriad BRCAAnalysis test. This result will confirm or determine patient eligibility. The second sample is required for a bridging study to validate the companion diagnostic test for olaparib (see [Section 6.6.2.1](#) below).

All patients must have a known deleterious or suspected deleterious germline *BRCA* mutation to be randomised; this may have been determined by local genetic testing prior to study entry or may be assessed as part of the enrolment procedure for the study (via a central testing by Myriad), see [Section 6.2.1](#). The specific *gBRCA* alteration on which eligibility is based must be entered into the trial database by selecting the appropriate value from the drop down menu. If the central laboratory analysis does not confirm a local *gBRCA* determination, that information should also be entered in the eCRF, along with indication of whether or not the patient was enrolled into the trial.

Residual blood (or its derivatives) may be used to evaluate future *BRCA* companion diagnostic tests and for additional exploratory work, to elucidate the mechanism of response, understand the mode of action of study treatment, and improve the understanding of disease recurrence (including *BRCA* mutation status and its role in response).

For blood volume see [Section 7.1](#).

6.6.2.1 Collection of a blood sample for assessment of current and future *BRCA* mutation assay(s)

At the time that the sample is collected for shipment to Myriad for central testing, all patients will be required to provide a second mandatory 9 ml blood sample that will be stored for subsequent assessment of current and future *BRCA* mutation assay(s).

Samples may also be used to investigate future *BRCA* mutation assays as well as mutations in other genes known/predicted to have a role in breast cancer.

Please refer to the B-55/6-13 Pathology and Correlative Science Instructions for further details of archival tumour collection, shipping and storage.

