12.1.1 Full analysis set

Intention to treat (ITT): The primary statistical analysis of the efficacy of olaparib will include all randomised patients and will compare the treatment groups on the basis of randomised

treatment, regardless of the treatment actually received. Patients who were randomised but did not subsequently go on to receive study treatment are included in the Full Analysis Set (FAS).

For the interim analysis two efficacy populations will be defined.

1. ITT population: This will include all randomised patients and will compare the treatment groups on the basis of randomised treatment, regardless of the treatment actually received. Note: it is anticipated that all patients will be randomised by the time of the interim analysis.
2. Mature cohort ITT population: This will include the first 900 randomised patients only and will compare the treatment groups on the basis of randomised treatment, regardless of the treatment actually received.

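### Section 7.5 removes a randomised patient from the study for withdrawing BRCA-sample consent, contrary to Section 5.9, so follow-up of willing patients is lost

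*Protocol*

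**What the plan says.** Protocol Section 7.5 goes through the donated samples one by one and states what follows when consent for each is withdrawn. For the BRCA sample: "As collection of the biological samples is an integral part of the study, then the patient is withdrawn from further study participation". Section 6.6.2 shows what this covers: "Two blood samples are mandated for all patients", one for the central test and one stored for current and future assays.

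The other mandatory samples are treated differently in the same section. For archival tumour: "Although mandatory*, the patient may continue in the study if the patient is already randomised". For biomarker blood: "the patient may continue in the study despite withdrawing consent for analysis of the biomarker samples".

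Section 5.9 sets the general rule. A patient who gives up the full visit schedule but will still supply recurrence or survival information stays in the study, and "if a patient does not wish to have any further data collected, only then should they be considered as withdrawing consent from the study". Sample consent appears there only as a separate question for someone who has already withdrawn: "he/she should be specifically asked if they are also withdrawing consent to the use of any of their samples". It is not among the listed reasons for withdrawal from the study. Another listed reason, incorrect enrolment, is confined to the period before randomisation: "this option is only applicable to patients not randomised into the study".

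Section 12.1.1 defines the analysis: "The primary statistical analysis of the efficacy of olaparib will include all randomised patients".

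**The concern.** The two sections give opposite instructions for one patient: randomised, unwilling to have the BRCA sample used, willing to be followed. A site cannot obey both. If it obeys 7.5, follow-up stops for a reason unrelated to whether the patient would supply outcome data. IDFS is then censored at the last disease evaluation, DDFS at the last clinical examination and OS at the last date known alive (Sections 11.1.1 and 11.1.2). Under Section 5.9 withdrawn patients are not replaced.

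The situation can arise long after eligibility is settled. Section 6.6.2 allows residual blood to be used for later diagnostics and exploratory work, and Section 6.6.2.1 allows the second sample to be used for other genes. Section 7.2 allows samples for future research to be kept for up to 15 years after the last patient's last visit. A patient could object to these uses at any point in follow-up.

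**Working it through.** **Step 1. The provisions side by side, for a randomised patient.**

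| Situation | Section | Consequence |
|---|---|---|
| Withdraws BRCA-sample consent, accepts follow-up | 7.5 | Taken out of the study |
| Same patient | 5.9 | Stays in; has not refused further data collection |
| Withdraws archival tumour consent | 7.5 | May continue |
| Withdraws biomarker blood consent | 7.5 | May continue |
| Found ineligible, no agreement reached on treatment | 5.3 | Efficacy assessments continue unless consent is withdrawn |
| Local mutation not confirmed centrally | 6.2.1 | Only continuation of treatment is discussed; no study withdrawal prescribed |

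Rows 1 and 2 conflict. Rows 3 to 6 show that elsewhere the protocol keeps randomised patients under observation, even when they prove ineligible or the mutation is not confirmed. Row 1 is the exception.

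**Step 2. Reproduce the plan's own figure.** Inputs from Section 12.2.7: HR 0.7, 330 IDFS events, 1:1 allocation, two-sided 5%, 1800 patients.

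- Events for 90% power: 4 × (1.960 + 1.282)² / (ln 0.7)² = 331 after rounding up; the protocol states 330.
- Power with d events: Φ(|ln 0.7| × √d / 2 − 1.960). With d = 330: 0.3567 × 18.166 / 2 = 3.240; 3.240 − 1.960 = 1.280; Φ(1.280) = 0.8997, against a stated 90%.

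The figure reproduces, and this point does not change it.

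**Step 3. Range for IDFS.** The protocol gives no rate of BRCA-sample consent withdrawal, so the first column is assumed. Each patient is taken to leave at time zero and to carry the average event risk, 330/1800 = 18.3%. The events affected are k × 330/1800. The power column applies the Step 2 formula to 330 minus that number, as if the data cut-off date were fixed.

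| Patients removed, k (assumed) | Share of 1800 | IDFS events affected | Power at a fixed cut-off |
|---|---|---|---|
| 1 | 0.06% | 0.18 | 0.8995 |
| 5 | 0.28% | 0.92 | 0.8989 |
| 18 | 1% | 3.3 | 0.8968 |
| 36 | 2% | 6.6 | 0.8938 |
| 90 | 5% | 16.5 | 0.8845 |

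Leaving at time zero is pessimistic, because later removal loses less. The fixed cut-off is also not the protocol's rule: Section 12.2.1.1 triggers the primary analysis at a minimum of 330 observed events. The events would still be collected, slightly later, so the power column overstates the harm.

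**Step 4. OS.** Section 12.2.2 sets the final OS analysis at 10 years after the last randomisation, with no event target. Nothing there makes up for deaths that occur after removal. The protocol gives no death rate, so no number is attached.

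**The case against.** The strongest reply is that the BRCA sample really is different. Patients entered on a local result are randomised on that result, and Section 3.2.3 places central reconfirmation soon after randomisation, so the sample may still be untested at that point. The central result defines the confirmed-mutation sensitivity analyses of IDFS, DDFS and OS (Sections 12.2.1.2 and 12.2.2), and secondary objective 5 relies on current and future assays. This stands as a reason to call the sample integral. It does not show that outcome follow-up must end: a patient without a central result can be left out of that sensitivity analysis and still contribute to the primary one.

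A second reply is that the line was meant for patients still in screening, when the BRCA samples are taken. That is possible, but the text does not say so, and the next line of 7.5 makes exactly that distinction for archival tumour.

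A reader might infer more than the documents support:

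- *That ITT is broken.* It is not. Section 12.1.1 keeps every randomised patient, and Section 5.9 keeps and uses data obtained before withdrawal. Follow-up is lost, not membership of the set.
- *That IDFS events are lost and the primary analysis is underpowered.* The event trigger turns the loss mainly into delay.
- *That the censoring is informative because discordant central results reach the investigator.* Nothing links a discordant result to withdrawal of sample consent, and Section 12.2.4 expects very few discordant patients.
- *That after randomisation the samples have no further scientific use.* The uses listed above contradict this.

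**Conclusion.** The contradiction between Sections 7.5 and 5.9 is real in the current text. Followed as written, 7.5 ends follow-up of a randomised patient who is willing to be followed.

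The size is unknown and probably small. On the assumed rates, removing 1% of patients at time zero affects about 3.3 IDFS events and, even with a fixed cut-off, moves power only from 0.8997 to 0.8968. Because IDFS is event-driven, the practical effect there is a short delay and earlier censoring. Deaths after removal would be lost to the final OS analysis.

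This is a point of consistency and retention. It does not challenge the sample size, the error rate or the analysis population. It is worth correcting because the loss is avoidable and outcome data not collected may be unrecoverable. The conclusion rests on reading the BRCA line as covering all patients, which is what its wording does.

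**What to change.** Reconcile Section 7.5 with Section 5.9. For randomised patients, state that withdrawal of BRCA-sample consent leads to disposal of the sample, while follow-up for recurrence, new cancers and survival continues unless the patient refuses further data collection under 5.9. Add that a patient without a central result is left out only of the centrally confirmed gBRCA sensitivity analysis. If the present line was meant only for patients before randomisation, say so.

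The line as it stands also bears on study treatment for patients still within the treatment period. Whether treatment continues in such a patient is for the sponsor to reconcile and is not prescribed here.

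The cost is about one sentence in 7.5 and matching consent wording, with no new procedures.
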